### **ARM B: Nivolumab and ipilimumab should be delayed for the following:**

- Any Grade  $\geq$  2 non-skin, drug-related adverse event, with the following **exceptions**:
  - Grade 2 drug-related fatigue or laboratory abnormalities **do not require** a treatment delay.
- Any Grade 3 skin, drug-related adverse event.
- Any Grade 3 drug-related laboratory abnormality, with the following **exceptions** for asymptomatic amylase or lipase, AST, ALT, or total bilirubin:
  - Grade 3 amylase or lipase abnormalities that are not associated with symptoms or clinical manifestations of pancreatitis **do not require** a dose delay. It is recommended to consult with the sponsor-investigator for Grade 3 amylase or lipase abnormalities.
  - If a patient has a baseline AST, ALT, or total bilirubin that is within normal limits, delay dosing for drug-related Grade  $\geq$  2 toxicity.
  - If a patient has baseline AST, ALT, or total bilirubin within the Grade 1 toxicity range, delay dosing for drug-related Grade  $\geq$  3 toxicity.

### **11.3. Criteria to Resume Treatment**

When a patient's treatment with study drug is interrupted due to adverse event, the patient's treatment may be resumed when the drug-related AE(s) resolve to Grade ≤1 or baseline value, with the following exceptions:

- Patients may resume treatment in the presence of Grade 2 fatigue.
- Patients who have not experienced a Grade 3 drug-related skin AE may resume treatment in the presence of Grade 2 skin toxicity.
- Patients with baseline Grade 1 AST/ALT or total bilirubin who require dose delays for reasons other than a 2-grade shift in AST/ALT or total bilirubin may resume treatment in the presence of Grade 2 AST/ALT OR total bilirubin.
- Patients with combined Grade 2 AST/ALT AND total bilirubin values meeting discontinuation parameters ([Section 11.4](#)) should have treatment permanently discontinued.
- Drug-related pulmonary toxicity, diarrhea, or colitis, must have resolved to baseline before treatment is resumed. Patients with persistent Grade 1 pneumonitis after completion of a steroid taper over at least 1 month are eligible for retreatment at the discretion of the investigator.
- Drug-related endocrinopathies adequately controlled with only physiologic hormone replacement may resume treatment.
- Patients in Arm A may resume treatment with relatlimab when troponin levels return to normal.

If the criteria to resume treatment are met, the subject should restart treatment at the next scheduled time point per protocol. However, if the treatment is delayed past the scheduled time point per protocol, the scheduled study treatment administration will be delayed, but not skipped, until dosing resumes. In particular, this is to ensure that subjects in Arm B will receive 4 administrations of combined nivolumab and ipilimumab treatment if toxicity allows.

If dose delay is necessary for subjects in Arm B during Weeks 1-12 (i.e. Cycles 1 thru 4), then both nivolumab and ipilimumab must be delayed until treatment can resume. However, if a nivolumab-related infusion reaction prevents subsequent infusion of ipilimumab on the same day, the dose of ipilimumab should be replaced as soon as possible. In such instances, at least 19 days must elapse between the replacement dose of ipilimumab and the administration of the next dose of nivolumab combined with ipilimumab.

If treatment is delayed or interrupted for > 6 weeks, the subject must be permanently discontinued from study therapy, except as otherwise specified (e.g. in [Section 11.4](#)).

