  - If TnT or TnI levels are >1 to 2 $\times$  ULN within 24 hours, the subject may undergo a cardiac evaluation and be considered for treatment based on the discretion of the PI.
  - When repeat levels within 24 hours are not available, a repeat test should be conducted as soon as possible.
  - If TnT or TnI repeat levels beyond 24 hours are < 2 $\times$  ULN, the subject may undergo a cardiac evaluation and be considered for treatment, based on the discretion of the PI.
10. Arm A: Corrected QT interval (QTc) by Fridericia's method (QTcF) assessed by electrocardiogram (ECG) completed  $\leq$  28 days before initiation of protocol treatment ([Section 8.9](#)), and resulted as:
  - QTcF  $\leq$  480 msec
11. Tumor tissue from a biopsy or resection obtained since completion of the last systemic therapy must be available for analysis of MHC-II status and for biomarker analysis. If a sample is not available or if the quantity or quality of tissue is insufficient to provide adequate results, an additional biopsy may be performed for MHC-II analysis. Patients cannot be enrolled on the study unless MHC-II is known.
12. Women must not be breastfeeding.
13. A woman of childbearing potential (WOCBP) – see Appendix 4 for definition of WOCBP – must have a negative serum pregnancy test within 14 days prior to receiving first dose of protocol-indicated treatment, and must agree to follow instructions for using acceptable contraception ([Appendix 4](#)) from the time of signing consent, and for 165 days (24 weeks) after her last dose of protocol-indicated treatment.
14. A man able to father children (see Appendix 4 for definition) who is sexually active with a WOCBP must agree to follow instructions for using acceptable contraception ([Appendix 4](#)), from the time of signing consent, and for 225 days (33 weeks) after his last dose of protocol-indicated treatment.

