## **11.2. Criteria for Dose Delays**

Dose delay criteria apply for all adverse events deemed by the investigator to be possibly, probably or definitely drug-related, regardless of whether or not the event is attributed to nivolumab, ipilimumab, relatlimab, or combinations.

All study drugs (i.e. nivolumab, ipilimumab and relatlimab) must be delayed until treatment can resume (see [Section 11.3](#)).

Treatment delays up to 6 weeks from the last dose are allowable.

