### **ARM A: Nivolumab and relatlimab should be delayed for the following:**

- Select drug-related AEs and drug-related laboratory abnormalities:
  - $\geq$  Grade 3 skin.
  - $\geq$  Grade 1 pneumonitis.
  - $\geq$  Single grade increase shift in abnormality in AST, ALT, and total bilirubin.
  - $\geq$  Grade 2 creatinine.
  - $\geq$  Grade 2 diarrhea or colitis.
  - $\geq$  Grade 2 neurological AE.
  - Grade 4 amylase and/or lipase abnormalities regardless of symptoms or clinical manifestations.
- Myocarditis (any grade).
- All troponin elevations require a dose delay to allow for prompt cardiac evaluation. Following this evaluation, determination of further treatment will be based on the discretion of the investigator.
- Any AE, laboratory abnormality, or concurrent illness that, in the judgment of the investigator, warrants delaying the dose of study drug.

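### Arm A liver-test hold and resume criteria contradict each other for one-grade rises, and troponin has two different routes back to treatment

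*Combined protocol and SAP*

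**What the plan says.** **Liver tests, hold.** The Arm A list in Section 11.2 includes, among drug-related events, this trigger at or above: "Single grade increase shift in abnormality in AST, ALT, and total bilirubin". The opening of 11.2 says that all study drugs "must be delayed until treatment can resume" and points to 11.3 for when that is.

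**Liver tests, resume.** Section 11.3 gives a general rule: "the patient's treatment may be resumed when the drug-related AE(s) resolve to Grade ≤1 or baseline value, with the following exceptions". One exception concerns patients with Grade 1 AST/ALT or bilirubin at baseline. If they were delayed "for reasons other than a 2-grade shift in AST/ALT or total bilirubin may resume treatment in the presence of Grade 2" AST/ALT or bilirubin. Neither the general rule nor this exception is restricted to an arm.

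**Liver tests, Arm B.** Section 11.2 sets different triggers: "If a patient has a baseline AST, ALT, or total bilirubin that is within normal limits, delay dosing for drug-related Grade" 2 or above. With a Grade 1 baseline, the Arm B delay starts at Grade 3.

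**Troponin.** The Arm A list in 11.2 delays dosing for every troponin elevation so that the heart can be evaluated. After that, "determination of further treatment will be based on the discretion of the investigator". Section 11.3 says: "Patients in Arm A may resume treatment with relatlimab when troponin levels return to normal".

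**The concern.** A hold rule and a resume rule should not both be true of the same laboratory result. In Arm A they can be, because a trigger that fires on a one-grade rise is paired with a resume exception worded around a two-grade rise. Two sites could then act in opposite ways on the same value, and each could cite the protocol.

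The consequence is more than administrative. Sections 11.2 and 11.4 count the permitted delay as six weeks from the last dose, after which treatment stops permanently unless a listed exception applies. Arm A is dosed every 28 days. A hold that begins on a scheduled dosing day therefore has 42 − 28 = 14 days left. Which reading a site adopts can affect whether a patient stays on treatment. Safety and tolerability are secondary objectives, with about 18 patients per arm, so delay and exposure data would partly reflect how each site reads the text.

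For troponin the question is which section governs the return to treatment, and for which drug.

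**Working it through.** The plan states no figure to reproduce here. The check is logical: write the rules as conditions and look for grade changes where hold and resume are true together.

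Let *b* be the baseline grade (0 = normal) and *c* the current grade.

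- Arm A hold (11.2, Arm A list): c − b ≥ 1.
- Arm B hold (11.2, Arm B list): c ≥ 2 if b = 0; c ≥ 3 if b = 1. Arm B's baseline-specific liver triggers do not mention b = 2.
- General resume rule (11.3): c ≤ 1 or c ≤ b.
- Liver exception (11.3): b = 1, c = 2, and the reason for delay is not a two-grade shift.

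All upward changes from b = 0, 1 or 2 to a grade no higher than 4 number 4 + 3 + 2 = 9:

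| Baseline → current | Arm A hold | General resume | Liver exception | Arm B hold | Overlap |
|---|---|---|---|---|---|
| 0 → 1 | yes | yes | no | no | **Arm A** |
| 0 → 2 | yes | no | no | yes | none |
| 0 → 3 | yes | no | no | yes | none |
| 0 → 4 | yes | no | no | yes | none |
| 1 → 2 | yes | no | yes | no | **Arm A** |
| 1 → 3 | yes | no | no | yes | none |
| 1 → 4 | yes | no | no | yes | none |
| 2 → 3 | yes | no | no | not stated | none |
| 2 → 4 | yes | no | no | not stated | none |

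Arm A has two overlaps. For 0 → 1, the one-grade rise forces the hold, and Grade 1 already satisfies the general rule. For 1 → 2, the same kind of rise forces the hold, and because it is one grade rather than two it falls within the exception. Arm B has no overlap in the seven changes its triggers address: from either baseline it delays only at a shift of two grades or more. The two-grade wording in 11.3 therefore fits Arm B and not Arm A.

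Abnormal baseline values are admissible: Section 5.1 accepts AST and ALT up to 3.0 times the upper limit of normal (5.0 times with hepatic metastases) and bilirubin up to 1.5 times.

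Troponin, side by side:

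| | Section 11.2, Arm A | Section 11.3 |
|---|---|---|
| Drugs covered | nivolumab and relatlimab, both held | relatlimab only |
| Condition | investigator's decision after cardiac evaluation, no level given | return to normal |

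A value that is elevated has not returned to normal, so the troponin hold and this resume condition are never true together. What differs is the standard and the drug named.

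**The case against.** Several points on the other side deserve weight.

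- *Resolving implies improvement first.* This softens the 0 → 1 case. It does not reach the 1 → 2 case, because the exception permits resumption while Grade 2 is present and asks for no improvement.
- *The exception was meant for delays unrelated to the liver.* That is a plausible intention, but the words exclude only two-grade shifts, and a one-grade liver shift is something else.
- *Resumption is permissive, and Section 11 lets the physician delay for any laboratory abnormality.* True, so a cautious site can defend a longer hold. But 11.3 also says that a patient who meets the criteria should restart at the next scheduled point, so discretion does not settle which rule governs.
- *Serious liver toxicity is covered elsewhere.* This stands. The discontinuation limits in 11.4 are not in dispute; the conflict concerns one-grade, low-grade shifts.
- *The Appendix 6 hepatic algorithm may guide sites.* Its figure is not available in the text reviewed, so the practical effect cannot be judged fully. It would not change the wording of 11.2 and 11.3.
- *The troponin statements can be read together, as discretion exercised within a stated condition.* For relatlimab that is possible. It leaves nivolumab without a troponin condition in 11.3.

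A reader might infer stronger troponin claims. One is that a patient enrolled with raised troponin is caught by the same contradiction, since 5.1 says of some such patients that "the subject may undergo a cardiac evaluation and be considered for treatment based on the discretion of the PI". The documents do not establish this. Section 5.1 sets limits, repeat testing and evaluation; an entry limit and an on-treatment hold serve different purposes; and 11.2 introduces its delay criteria as applying to drug-related events, so a stable pre-treatment elevation is arguably outside them. Another is that the one fatal drug-related event reported with nivolumab plus relatlimab, a myocarditis, shows the danger of the inconsistency. It does not: Arm A dosing is delayed for myocarditis of any grade under 11.2, and Grade 3 requires discontinuation under 11.4.

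**Conclusion.** The liver-test contradiction holds on the literal text. In Arm A, a drug-related rise from normal to Grade 1 or from Grade 1 to Grade 2 meets the hold and resume rules together: two of nine upward grade changes, the second being the firmer case. The troponin point is narrower: two different standards for returning to treatment, one of which names only one of the two held drugs. It is not a same-moment overlap.

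This rests on reading the 11.3 rules as applying to both arms, which is how they are written, and on taking Grade 0 as a normal baseline. The nine changes are possible states, not patients, so two of nine is not a rate. The background table lists drug-related AST increase in 3.9% and ALT increase in 3.6% of 304 subjects, but those are reported adverse events rather than one-grade shifts, and they do not give the frequency of the conflict. No effect on the primary T-cell endpoint is shown. The point bears on patient safety and on the consistency of Arm A delay and exposure data, and it should be fixed.

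**What to change.** The clinical leads should reconcile the opening of Section 11.2, its Arm A list and Section 11.3 so that:

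- each Arm A liver-test trigger has one matching resume condition that a patient cannot already meet at the moment of the hold;
- the Grade 1 baseline exception states whether a one-grade liver shift counts among the reasons it covers;
- troponin has one stated route back to treatment, covering each held drug;
- every bullet in 11.3 says which arm and which drug it applies to.

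The Appendix 6 hepatic algorithm should be checked against the revised wording. This review does not say which threshold is right. The cost is a protocol wording change and a notice to sites; sample size, visits and analysis are unaffected.

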### **5.1. Inclusion Criteria**

Patients must meet all of the following inclusion criteria to be eligible for enrollment into the study:

1. Signed and dated written informed consent.
2.  $\geq 18$  years of age at the time of informed consent.
3. Eastern Cooperative Oncology Group (ECOG) performance status of 0 or 1.
4. Histologically confirmed locally advanced/unresectable or metastatic melanoma.
5. Patients who have received prior anti-CTLA-4 or anti-PD-1/PD-L1 for adjuvant treatment of melanoma are eligible if  $> 6$  months have elapsed between the last dose of adjuvant treatment and starting this study – provided there is no history of life-threatening toxicity related to such prior treatment, or such toxicity is unlikely to re-occur with standard countermeasures (e.g. hormone replacement after endocrinopathy).
6. Patients who have received adjuvant therapy with interferon and/or a BRAF inhibitor and/or MEK inhibitor for adjuvant therapy are permitted to enroll.
7. At least one measurable target lesion as defined by RECIST 1.1 which can be followed by CT or MRI.
  - If located in a previously irradiated area, a tumor lesion is considered a measurable/target lesion only if subsequent disease progression in the lesion has been documented at least 90 days following completion of radiotherapy.
8. Adequate organ and bone marrow function  $\leq 14$  days prior to first dose of protocol-indicated treatment:
  - White blood cell count (WBC)  $\geq 2,000/\text{mm}^3$ .
  - Absolute neutrophil count (ANC)  $\geq 1,500/\text{mm}^3$ .
  - Platelets  $\geq 75,000/\text{mm}^3$ .
  - Hemoglobin  $\geq 8.0 \text{ g/dL}$ .
  - Serum creatinine  $\leq 2.0x$  upper limit of normal (ULN), or calculated creatinine clearance (CrCl)  $> 40 \text{ mL/min}$  per the Cockcroft-Gault formula ([Appendix 1](#)).
  - Total bilirubin  $\leq 1.5x$  ULN  
(except patients with Gilbert Syndrome, who must have total bilirubin  $< 3.0 \text{ mg/dL}$ ).
  - AST (aspartate aminotransferase) and ALT (alanine aminotransferase)  $\leq 3.0x$  ULN ( $\leq 5.0x$  ULN in those with hepatic metastases).

9. Acceptable troponin level  $\leq$  14 days prior to first dose of protocol-indicated treatment:
  - Troponin T (TnT) or I (TnI)  $\leq$  2 $\times$  institutional ULN.
  - Subjects with TnT or TnI levels between >1 to 2 $\times$  ULN will be permitted if repeat levels within 24 hours are  $\leq$  1 $\times$  ULN.

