#### **11.4. Criteria to Permanently Discontinue Treatment**

Treatment with nivolumab, ipilimumab, and/or relatlimab (BMS-986016) should be permanently discontinued for the following:

- Any Grade 2 drug-related uveitis or eye pain or blurred vision that does not respond to topical therapy and does not improve to Grade 1 severity within the re-treatment period OR requires systemic treatment.
- Any Grade 3 non-skin, drug-related adverse event lasting > 7 days, with the following exceptions for drug-related laboratory abnormalities, endocrinopathies, uveitis, pneumonitis, bronchospasm, diarrhea, colitis, neurologic toxicity, hypersensitivity reactions, and infusion reactions:
  - Grade 3 drug-related uveitis, pneumonitis, bronchospasm, diarrhea, colitis, neurologic toxicity, hypersensitivity reaction, or infusion reaction of any duration **requires** discontinuation.
  - For Grade 3 endocrinopathy adverse events such as adrenal insufficiency, ACTH deficiency, hyper- or hypothyroidism, or glucose intolerance, which resolve or are adequately controlled with physiologic hormone replacement (steroids, thyroid hormones) or glucose controlling agents, respectively, **do not require** treatment discontinuation.
  - Grade 3 drug-related laboratory abnormalities **do not require** treatment discontinuation **except**:
    - Grade 3 drug-related thrombocytopenia > 7 days or associated with bleeding **requires** discontinuation.
    - Any drug-related liver function test (LFT) abnormality that meets the following criteria **requires** discontinuation:
      - AST or ALT > 5 x ULN.
      - Total bilirubin > 3 x ULN.
      - Concurrent AST or ALT > 3 x ULN and total bilirubin > 2 x ULN.
- Any Grade 3 myocarditis.
- Any Grade 4 drug-related adverse event or laboratory abnormality, **except for the following events** which do not require discontinuation:
  - Grade 4 amylase or lipase abnormalities that are not associated with symptoms or clinical manifestations of pancreatitis. It is recommended to consult with the sponsor-investigator for Grade 4 amylase or lipase abnormalities.
  - Isolated Grade 4 electrolyte imbalances/abnormalities that are not associated with clinical sequelae and are corrected with supplementation/appropriate management within 72 hours of their onset.
- Any dosing interruption lasting > 6 weeks from the last dose **with the following exceptions**:

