  - Dosing interruptions to allow for prolonged steroid tapers to manage drug-related adverse events are allowed. Prior to re-initiating treatment in a subject with a dosing interruption lasting > 6 weeks from the last dose, the sponsor-investigator must be consulted in writing. Tumor imaging assessments should continue as per protocol even if dosing is interrupted.

---

- Dosing interruptions > 6 weeks from the last dose that occur for non-drug-related reasons may be allowed if approved by the sponsor-investigator. Prior to re-initiating treatment in a subject with a dosing interruption lasting > 6 weeks from the last dose, the sponsor-investigator must be consulted. Tumor imaging assessments should continue as per protocol even if dosing is interrupted.

Any adverse event, laboratory abnormality, or intercurrent illness which, in the judgment of the Investigator, presents a substantial clinical risk to the patient with continued study drug dosing should discontinue the study drugs.

The consideration to re-initiate study therapy in selected cases at any time point after discontinuation could be made on a case-by-case basis after considering the overall benefit/risk profile and in consultation between the investigator and the sponsor-investigator. The selected patients will need to meet eligibility criteria. The original dose and schedule and protocol rules would apply accordingly ([Section 11.4](#)).

In this trial, combinatorial treatment with relatlimab and nivolumab (Arm A) or ipilimumab and nivolumab (Arm B) shall be considered separable (see also [Section 9.9](#)):

- **Arm A:** The assessment for discontinuation of drug should be made separately considering each drug component in the nivolumab + relatlimab combination (Arm A). If discontinuation criteria are attributed to only one drug used in this combination, once the patient meets criteria to resume therapy, the subject may continue dosing with nivolumab (if nivolumab was not attributed to criteria for discontinuation) and/or with relatlimab (if relatlimab was not attributed to criteria for discontinuation).

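### In Arm A, a drug-related liver value that rises from baseline Grade 1 to Grade 2 triggers the 11.2 hold, but 11.3 permits resumption at that same value, so the two sections require no liver recovery before re-dosing

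*Combined protocol and SAP*

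**What the plan says.** Section 11.2 sets separate liver triggers for the two arms.

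- **Arm A.** Both drugs are delayed for a drug-related rise of at least one grade, worded as "Single grade increase shift in abnormality in AST, ALT, and total bilirubin". The trigger does not depend on the baseline grade.
- **Arm B.** A patient with normal baseline values is held at drug-related Grade 2 or higher. For a raised baseline the text reads "If a patient has baseline AST, ALT, or total bilirubin within the Grade 1 toxicity range, delay dosing for drug-related Grade" 3 or higher.

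For either arm, "All study drugs (i.e. nivolumab, ipilimumab and relatlimab) must be delayed until treatment can resume", with a pointer to 11.3.

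The general rule in 11.3 allows treatment to resume once drug-related events are back to Grade 1 or lower, or to the baseline value. A list of exceptions follows. The third covers patients with Grade 1 baseline AST/ALT or total bilirubin. Those held for "reasons other than a 2-grade shift in AST/ALT or total bilirubin may resume treatment in the presence of Grade 2" values of these tests. It names no arm, whereas the troponin exception in the same list is expressly for Arm A.

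Two outer limits apply. Section 11.4 stops treatment permanently for "Any drug-related liver function test (LFT) abnormality that meets the following criteria": AST or ALT above 5x ULN, total bilirubin above 3x ULN, or both together above 3x and 2x ULN. After a delay of more than 6 weeks, "the subject must be permanently discontinued from study therapy", unless an exception in 11.4 applies.

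**The concern.** The Arm A trigger is stricter than the Arm B trigger: a single-grade rise is enough whatever the baseline. The shared resume rule appears to undo it for one group, Arm A patients who enter with Grade 1 liver values and rise to a drug-related Grade 2. For them 11.2 says hold and 11.3 says treatment may resume, on the same laboratory result.

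At stake is consistent safety management. Two sites could each follow the protocol, one giving nivolumab and relatlimab at a Grade 2 value and the other waiting for recovery.

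**Working it through.** The plan gives no figure to reproduce here, so the check sets the hold rule beside the resume rule.

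**Can the case occur?** Yes. Inclusion criterion 8 in Section 5.1 admits AST and ALT up to 3.0x ULN (5.0x with hepatic metastases) and total bilirubin up to 1.5x ULN. Sections 11.2 (Arm B) and 11.3 both provide for patients with Grade 1 baseline values.

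**Are the two rules read against the same value?** Generally, yes. The opening of Section 11 says that an event causing a delay should usually be present on the intended dosing day. Arm A chemistries are scheduled on Day 1 (Section 7.2).

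**Pairs at Grade 2 or below.** Grade 0 means normal, and all values are drug-related.

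| Arm | Baseline to current grade | 11.2 hold? | 11.3 already met at that value, as written? | With the third bullet limited to Arm B |
|---|---|---|---|---|
| A | 0 to 1 | Yes | Yes, general rule | Yes, general rule |
| A | 0 to 2 | Yes | No | No |
| A | 1 to 2 | Yes | **Yes, third bullet** | **No** |
| B | 0 to 1 | No | n/a | n/a |
| B | 0 to 2 | Yes | No | No |
| B | 1 to 2 | No | n/a | n/a |

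In Arm A, holds already met at the triggering value number 2 of 3 as written and 1 of 3 after the change. In Arm B they number 0 of 3 both ways. A rise to Grade 3 from a lower grade in Arm A, or from normal or Grade 1 in Arm B, is held and not released at that value under either wording.

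**Why the bullet fits Arm B only.** The smallest shift that triggers an Arm B liver hold is 2 − 0 = 2 grades from normal and 3 − 1 = 2 grades from Grade 1. Excluding two-grade shifts therefore leaves the Arm B liver holds intact. The bullet then covers Arm B patients held for something else whose Grade 2 value would not itself have caused a hold. In Arm A the trigger is a shift of 1, which the exclusion does not reach.

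**Longest added delay.** The limit is 42 days from the last dose and the Arm A cycle is 28 days, so 42 − 28 = 14 days past the planned Day 1. It can be longer only under the 11.4 exceptions.

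**Effect on the biopsy.** C2D1 falls 28 days after C1D1. A 14-day hold moves the second dose to day 28 + 14 = 42 after C1D1. The Arm A biopsy (Section 8.13) is due at C2D15, which is 28 + 14 = 42 days after C1D1, with a window of ±7 days (35 to 49). Section 11 keeps other procedures on their original timeline during a hold, so the biopsy could follow one dose instead of two.

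**Number affected.** The share with a Grade 1 baseline is not given. As a rough guide, Table 2 reports drug-related AST increase of any grade in 12/304 (3.9%) and ALT increase in 11/304 (3.6%). Applied to 18 Arm A patients, that is 18 × 12/304 = 0.7 and 18 × 11/304 = 0.7, before requiring a Grade 1 baseline and a rise to Grade 2. This assumes that rates from that study carry over to this trial.

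**The case against.** A reader might infer that the Arm A hold lasts zero days or has no effect. The documents do not support that. The bullet is permissive. Section 11 and the last Arm A item in 11.2 let the investigator delay for any laboratory abnormality. Section 11.3 restarts dosing at the next scheduled time point, which could be read as the next cycle. What stands is narrower: no wait in 11.2 or 11.3 is tied to liver recovery.

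A reader might also infer that, below the 11.4 limits, only 11.2 and 11.3 decide. That is too strong. Section 11.6 recommends the nivolumab-based algorithms in Appendix 6, including a hepatic one. Its figure is not shown in the text reviewed and may address Grade 2 values. Both 11.6 and the appendix describe the algorithms as guidance, so they would not remove the contradiction in the rules.

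The bullet may have been meant only for holds with a non-liver cause. It does not say so. Even on that reading, an Arm A patient could resume at a drug-related Grade 2 value for which 11.2 separately requires a hold.

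Finally, the correction puts patients with a Grade 1 baseline and a persistent Grade 2 value at risk of the 6-week limit. That is a fair objection. Accepting the risk is a clinical judgement for the sponsor-investigator.

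**Conclusion.** The conflict is in the text and is confined to one case: Arm A, baseline Grade 1, drug-related rise to Grade 2, below the 11.4 limits. A patient with normal baseline values who reaches Grade 2 is not covered by the bullet and must return to Grade 1 or lower. The conclusion rests on reading the bullet literally for both arms and on reading hold and resume against the same dosing-day value.

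This is a minor safety-rule correction. The number affected cannot be derived and is probably small. The current wording has no effect on power or on the planned primary analysis. It would be wrong to infer that liver toxicity goes unchecked, because 11.4 still stops treatment at its stated limits.

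**What to change.** Begin the third bullet of 11.3 with 'Arm B:'. Arm A liver holds then end under the existing general rule: Grade 1 or lower, or baseline value. That rule concerns drug-related events only, so a Grade 2 value from another cause would not block resumption. No hold trigger changes, and no Arm B outcome changes. While amending, check the Appendix 6 hepatic algorithm for consistency.

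The change does not touch the Arm A hold for a rise from normal to Grade 1, which already meets the general rule. Requiring a return to baseline grade there is not proposed. A persistent drug-related Grade 1 value could then run to the 6-week limit, and 11.4 excepts only interruptions for non-drug-related reasons and steroid tapers ("Dosing interruptions to allow for prolonged steroid tapers to manage drug-related adverse events are allowed").

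Costs:

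- A few Arm A patients are held longer, some to the 6-week limit (14 days past the planned Day 1, longer only under the 11.4 exceptions).
- An Arm A patient with a Grade 1 baseline who is held for another reason could no longer resume at a drug-related Grade 2 liver value. This agrees with the Arm A trigger.
- Held patients need unscheduled repeat liver panels.
- A patient held at C2D1 may have the primary-endpoint biopsy after one dose instead of two. The dose count at biopsy should be recorded.

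No extra patients are needed.
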